6.6.4 Follow-up

The time point for follow-up will be six weeks and one, two and five years after the operation. This is an established pattern for follow-up after bariatric surgery, and patients in this study will not deviate from this. Primary outcome is continuous use of ARM due to reflux symptoms at two years after surgery, or reoperation due to GORD within two years postoperatively. This should be a sufficient period of time to represent a realistic test of the performance of the study treatment, and allow any risks associated with potentially adverse effects over that period to be identified and assessed. One-year data will not be published separately. This is partly because it is generally not recommended to publish data for outcome with less than two-year follow after bariatric surgery, and partly because according to the literature there is an increase in the use of ARM after LSG also between one and two years postoperatively.

	RESEARCH PROTOCOL
Version no 4.0	Clinical intervention study

The follow-up visit at one, two and five years will include collection of the same data as for baseline, but gastroscopy and pH-metry will only be performed at the two-year follow-up. PRO-data at follow-up will be collected internet-based if possible.

6.6.5 Follow-up medical care

All patients having participated in the study will receive medical care and follow-up as all other patients according to national and/or hospital routine.

7 STATISTICAL CONSIDERATIONS

7.1 Statistical design

Patients will be allocated in a 1:1 fashion between LSG and LSGG. Participating hospitals will administer this by block randomization with 10 patients (i.e. 5 LSG, 5 LSGG) in each block. Group allocation will be determined by opening of sealed envelopes. The envelopes will be distributed to participating hospitals from SOReg-N.

All patients will be given a unique patient number, and SOReg-N will be informed regularly about group allocation.

Analysis for outcome will be performed according to ITT. All patients will thus be analysed within the allocated group. Missing data at two and five years will be handled by multiple imputation. The main analysis for outcome will be based on logistic mixed effect models with odds ratio between groups corrected for age, smoking and surgeon. A sensitivity analysis including hospitals will also be performed.

Information on group allocation will be blinded to patients and researchers.

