5.1.5 Measures to minimise bias

The study is a multicentre study with participating hospitals from at least two countries (Norway and Sweden). Patients will be allocated by randomization, and patients, health care workers and investigators will be blinded. The surgeons operation note will state that "randomization was performed according to protocol" and will not contain information on whether gastropexy was performed or not. The study coordinator at each hospital will be responsible for keeping an updated list of patients participating in the study including who has received a pexy or not. This information must be stored at a safe place and in such a way that it can be made available for caregivers if deemed necessary. An updated list should be sent to SOReg-N on the first day of every month (see also 6.6.2).

All details regarding surgical technique except whether a pexy was performed or not must be registered in SOReg. To adjust for possible surgeon-related influence on outcome, a code number must be registered in SOReg for the individual main operating surgeon. A code number will be administered from SOReg-N to qualified surgeons whom will receive an envelope containing five numbers, and each participating surgeon within that hospital must draw one number after having been certified either by the study administrator or by a locally qualified surgeon. In Sweden the prefix for each number will be "S" and in Norway "N". The individual surgeon must use the same code number during the whole study period. Patients will be informed about the importance of follow-up both for clinical and investigational reasons. For PRO, one reminder will be send to non-responders.

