5.1.6 Including more subjects to compensate for drop-outs

If the recruitment of patients are lower than expected in Norway and Sweden, hospitals in other countries (primarily Netherland) will be invited to participate.

In order to reduce drop-outs, patients will be randomized in the operating room after being anesthetized and after the surgeon has decided to proceed with a LSG, but before surgery starts. Randomization will be performed by the use of sealed envelopes containing information on group allocation. Any patient who has signed for participation but are withdrawn before randomization will be replaced by one new subject. A list of patient(s) who withdraw after inclusion must be kept at the participating hospital and the reason for withdrawal must be stated. This list should be presented to SOReg-N on the first day of every month (see also 6.6.2).

Patients who withdraw or are withdrawn from the study after randomization cannot be replaced.

	RESEARCH PROTOCOL
Version no 4.0	Clinical intervention study

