Each participating hospital will point out one person to coordinate the study within that hospital. This includes patient recruitment, obtaining written informed consent, local data management, correspondence with the national coordinator and with the Project Leader / institution responsible for this study. All included patients will be given a unique patient ID number. This number is the ID that is generated automatically by SOReg. All included patients in Sweden will thus have a six digits code number and all included patients in Norway will have a five digits code number. An updated list of included patients with overview of group allocation must be kept in a safe place within the hospital. A copy of this list containing the patient ID (no name or other identifiable data) shall be sent to SOReg-N on the first day of every month (see also 5.1.5 and 5.1.6 and appendix 17.6). Hospitals participating in the Bravo-arm of the study must balance the number of patients themselves so that an equal number of patients are allocated to the pexy and no-pexy group, respectively.

6.6.3 Factors that may compromise the outcome of the clinical study / interpretation of the results

This study is a randomized trial where the patients will be randomized into two groups. Potential differences between the groups like age, preoperative use of ARM and smoking will be accounted for by statistical methods.

Potential differences in performance between surgeons will be explored and adjusted for by statistical methods if found.

Missing values at two years will be accounted for by multiple imputation as necessary. Missing value at baseline will exclude the patient from the study.

Potential differences in culture and tradition between hospitals and countries for prescribing ARM, and similarly potential differences among patients demand for having ARM will be sought overcome by standardizing the information: ARM used in conjunction with the operation should be stopped at the latest by four weeks postoperatively. Patients using ARM after this period should actively be asked about this at the first follow-up (usually six weeks), and if no obvious reason exists it should be stopped. Similarly, if a patient is using ARM at the one-, two- or five year follow-up, the reason for this should be addressed.

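### A constant block of 10 per hospital, with the by-arm list kept by the coordinator who recruits, lets that person know about one assignment in six in advance

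*Protocol*

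**What the plan says.** Allocation is 1:1 (section 7.1): "Patients will be allocated in a 1:1 fashion between LSG and LSGG". The same section sets the block: "Participating hospitals will administer this by block randomization with 10 patients (i.e. 5 LSG, 5 LSGG) in each block". No other block size is mentioned.

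The mechanism is an envelope opened locally. Section 5.1.6: "Randomization will be performed by the use of sealed envelopes containing information on group allocation". Section 7.1: "The envelopes will be distributed to participating hospitals from SOReg-N".

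Two passages describe who knows past allocations. Section 5.1.5 makes the study coordinator at each hospital "responsible for keeping an updated list of patients participating in the study including who has received a pexy or not". Section 6.6.2 describes the person each hospital appoints to coordinate the study: "This includes patient recruitment, obtaining written informed consent, local data management". It also keeps the list showing group allocation inside the hospital, with a monthly copy to SOReg-N. The monthly form in appendix 17.6 sorts patient numbers into pexy and no pexy.

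One safeguard is stated, in section 5.1.6: "patients will be randomized in the operating room after being anesthetized and after the surgeon has decided to proceed with a LSG". Section 5.1.5 adds that the arm stays out of the operation note and out of SOReg, and that the list is stored safely.

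**The concern.** Sealed envelopes protect a trial only while nobody who influences entry can tell what the next one contains. With a constant block size, a person who knows the size and has the past allocations can count down the open block. Once one arm has used its five places, every remaining envelope in that block is known. Before that point, the arm with more places left is the better guess.

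Here the person who recruits and takes consent is also the person who keeps the count. At stake is the comparability of the arms. The primary endpoint is use of acid-reducing medication for reflux, or reoperation for reflux. Patients who already use such medication for reflux are eligible, and recruiters can see that use. It is therefore an obvious characteristic on which entry could be steered. Section 6.6.3 says that preoperative use will be accounted for, but the main model in section 7.1 lists only age, smoking and surgeon.

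**Working it through.** The protocol gives no figure for predictability, so there is none to reproduce.

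**Inputs**
- Block: 10, with m = 5 per arm, per hospital (section 7.1).
- Total randomized: 900 (section 7.4). Per hospital: 10 to 200 (section 7.12).
- Observer: someone who knows the block size and every earlier allocation in the open block.

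**1. Assignments known with certainty.** The last r places of a block are all one arm with probability 2·C(10−r, 5)/C(10, 5), where C(10, 5) = 252. In that case the first of those r places is already certain.

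| Place in block | r | Probability that it is known beforehand |
|---|---|---|
| 10th | 1 | 252/252 = 100% |
| 9th | 2 | 112/252 = 44.4% |
| 8th | 3 | 42/252 = 16.7% |
| 7th | 4 | 12/252 = 4.8% |
| 6th | 5 | 2/252 = 0.8% |

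The sum is 420/252 = 1.667 per block, which agrees with 2m/(m+1) = 10/6. As a share this is 16.7%. For 900 patients in 90 complete blocks it is 90 × 1.667 = 150. For a hospital with 200 patients it is 20 × 1.667 = 33.

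**2. Effect of incomplete final blocks.** A final block stopped after 7 patients contributes 14/252 = 0.06 certain assignments, where one sixth of 7 would be 1.17. One stopped after 8 contributes 56/252 = 0.22, against 1.33. In both cases the loss is 1.11, and no other stopping point loses more. The total is therefore at least 150 − 1.11 × (number of hospitals). The protocol does not give the number of hospitals. Under assumed numbers the lower bound is about 139 with 10 hospitals, 128 with 20 and 117 with 30.

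**3. Best guess.** If the observer always names the arm with more places left, the expected number correct per block is m + 2^(2m)/(2·C(2m, m)) − 1/2 = 5 + 1024/504 − 0.5 = 6.53. That is 65.3%, against 50% by chance.

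**4. Effect of varying the block size.** This was simulated with 300 sequences of 100 assignments and an observer who knows the mix of sizes and holds the list. The mixes are assumptions.

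| Block sizes | Certain | Best guess correct |
|---|---|---|
| 10 only | 16.5% (exact 16.7%) | 65.4% (exact 65.3%) |
| 4, 6, 8, 10 | 1.3% | 66.7% |
| 6, 8, 10, 12 | 1.1% | 65.6% |

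Varying the size removes nearly all certain assignments. It does not reduce the guessing advantage of someone who has the list.

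**The case against.** The strongest reply is section 5.1.6. Consent has been given, the patient is anaesthetized and the surgeon has decided to proceed before the envelope is opened. Screening tests may be up to six months old, so at consent the coordinator would have to foresee the patient's place in the block on the day of operation. This stands in large part: steering at first approach or consent is hard. It does not cover what happens close to surgery. Theatre order, late withdrawal and the decision to proceed all come before opening, and all can be influenced by an arm predicted from the list. Section 5.1.6 also replaces a consented patient who is withdrawn before randomization, so such a removal costs no sample size. The monthly withdrawal list with reasons is some check. But it concerns withdrawal after inclusion, and section 4 equates inclusion with randomization, so it is unclear whether it captures these patients.

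A reader might infer that anyone at a site can count the block, or that the surgeon sees every allocation. The documents do not support that. Section 5.1.5 foresees several surgeons per hospital, each of whom necessarily learns only the arms of their own patients. It also restricts the list and keeps the arm out of the notes. The full count belongs to the coordinator, or to a sole operating surgeon at a small site.

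A reader might also infer that concealment has failed and the comparison is biased. Predictability is an opportunity and does not show that anyone used it. Baseline use of acid-reducing medication is put at about 6% in section 7.2, or about 54 of 900, which limits how far steering on that factor alone could go. No effect on the odds ratio can be derived from the protocol.

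**Conclusion.** The point holds as an avoidable risk of selection bias. Followed as written, the protocol lets one identifiable person per hospital know 16.7% of assignments in advance and guess about 65% correctly. The figure of about 150 of 900 is an upper one: it assumes complete blocks, and a person who has the full list and knows the block size. It also rests on reading the study coordinator of section 5.1.5 and the hospital coordinator of section 6.6.2 as the same person, which is the natural reading.

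Section 6.6.2 adds to local use of the allocations. It says that hospitals in the Bravo part "must balance the number of patients themselves so that an equal number of patients are allocated to the pexy and no-pexy group", which presupposes that someone there works from the by-arm count.

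Confidence is high for the predictability and moderate for its consequence. A statistical analysis plan could not remove the weakness, because block size and list-keeping act before any data are analysed.

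**What to change.** 1. **Separate the list from recruitment.** Amend sections 5.1.5 and 6.6.2 so that the by-arm list is held by someone who does not recruit, consent or schedule. This could be SOReg-N or an existing staff member with no recruiting role. Keep the access for unblinding a single patient that sections 5.1.5 and 14.2 already require. The same person would handle the Bravo balancing.
2. **Vary and withhold the block size.** From the next block at each hospital, SOReg-N issues permuted blocks of randomly varying size within hospital, for example 6, 8, 10 and 12. Section 7.1 as seen by the sites should say only that permuted blocks within hospital are prepared centrally, with sizes documented elsewhere.

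Step 1 is essential, because step 2 alone leaves a list-holder guessing correctly about 66% of the time. Step 2 is what helps at a site with a single surgeon, who learns each arm by operating; some guessing advantage remains there.

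The cost is new envelope packs, a short amendment, a small change in who keeps the list, and a slightly larger possible imbalance within a hospital at the end of accrual. The sample size of 900 is unaffected.

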7.2 Sample size

LSGG are presently being performed in a small minority of hospitals in Norway, but the technique used differs between hospitals and surgeons making the results difficult to interpret. However, in order to avoid a potential influence from these hospitals on the power calculations, these hospitals have been excluded from this sample size evaluation.

The sample size calculation is based on stipulated changes in the use of ARM since we gather this as the most relevant known clinical variable reflecting patients symptoms.

According to recent, unpublished data from SOReg-S and SOReg-N, we find a three-fold increase in the use of ARM from preoperatively until two years after LSG for both countries. The prevalence of ARM-use before LSG however differs between the countries: In Norway, approximately 7% of the patients are using ARM on a daily basis while the corresponding figure in Sweden is approximately 5%.

In Norway, the use of ARM increase from 7 % to approximately 20 % as a mean observed at the two-year follow-up, while in Sweden the corresponding numbers are 5 % increasing to approximately 13%.

Since the population and number of hospitals performing bariatric surgery in Sweden is about twice that of Norway, we estimate a 2:1 composition of participants. Hence, the composite figures will be ≈ 6 % at baseline, increasing to ≈ 16 % at two years.

In order to account for a potential improvement in the LSG-group because of participation in a study (the Hawthorn-effect), the estimated rate for ARM-use in the LSG-group at two years will be set at 14 %.

	RESEARCH PROTOCOL
Version no 4.0	Clinical intervention study

According to the clinical experience encountered by [name] et al, adding gastropexy to the LSG reduced a rise in the use of PPI from preoperatively until two years. Stipulating a change from 6 to 14% in the LSG group, and from 6 to 7% in the LSGG-group, this will require a total of 686 patients using power 1 - beta = 85%.

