7.3 The level of significance and power of the clinical study

We have used the significance level of alpha = 5 % and power 1 - beta = 85 %.

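### The main model in 7.1 omits preoperative ARM use, which 6.6.3 says will be accounted for, and the two sections give different rules for surgeon adjustment

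*Protocol*

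**What the plan says.** Protocol 7.1 (Statistical design) states the primary analysis: "The main analysis for outcome will be based on logistic mixed effect models with odds ratio between groups corrected for age, smoking and surgeon". It adds, for centre: "A sensitivity analysis including hospitals will also be performed".

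Protocol 6.6.3 (factors that may compromise the outcome or its interpretation) says: "Potential differences between the groups like age, preoperative use of ARM and smoking will be accounted for by statistical methods". On operators it says: "Potential differences in performance between surgeons will be explored and adjusted for by statistical methods if found".

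Randomization is described in 7.1: "Participating hospitals will administer this by block randomization with 10 patients (i.e. 5 LSG, 5 LSGG) in each block". No stratification by preoperative ARM use is mentioned.

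The planning assumptions in 7.2 are framed as change from baseline: "Stipulating a change from 6 to 14% in the LSG group, and from 6 to 7% in the LSGG-group". Section 5.1.2 defines the endpoint as daily ARM use or reoperation for reflux disease. Section 6.5.2 excludes patients who take ARM for reasons other than reflux. Sections 7.10 and 7.11 exclude patients with missing baseline data.

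**The concern.** Age and smoking carry over from 6.6.3 to 7.1, but preoperative ARM does not. No other section restores it as a covariate. Section 7.10 uses baseline data only to impute missing outcomes, which does not adjust the comparison between arms.

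Of the three variables that 6.6.3 names, this one is closest to the outcome. A patient on daily ARM for reflux before surgery is already in the state that counts as failure at two years. Since randomization does not balance it, only the model can use it. Two things are at stake: precision in the primary comparison, and which odds ratio the trial will report, because a model with baseline ARM estimates a different conditional odds ratio from one without it.

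The surgeon wording is a second, smaller mismatch. Under 7.1 surgeon is always in the model; under 6.6.3 it enters only after the data have been inspected.

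**Working it through.** **1. The plan's own figure.** Inputs: 14% v 7% at two years (7.2), 1:1 allocation (7.1), alpha 5% and power 85% (7.3). Two-sided testing is assumed, since the protocol does not state sidedness. With pooled variance and no continuity correction:

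n per arm = [1.960·√(2·0.105·0.895) + 1.036·√(0.14·0.86 + 0.07·0.93)]² / 0.07² = (0.8497 + 0.4464)² / 0.0049 = 342.8, so 343 per arm and **686** in total. With 20% dropout, 686/0.80 = 857.5, so **858**. Both match 7.2 and 7.4. The 900 patients to be randomized leave 720 evaluable, with unadjusted power of 86.7%. The stated power therefore does not rest on any covariate.

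**2. What baseline ARM would add.** Baseline prevalence is 6% (7.2). The share q of baseline users in the control arm still on ARM at two years is not in the protocol, so it is **assumed** over 30% to 90%. To keep the control risk at 14%, the risk in non-users is r = (0.14 − 0.06q)/0.94. One common odds ratio for users and non-users is then solved so that the LSGG risk is 7%. The marginal odds ratio is (0.07/0.93)/(0.14/0.86) = 0.46. Simulation used 4,000 runs per scenario and a logistic model with and without baseline ARM; age, smoking and surgeon were not simulated.

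| q | r | Conditional OR | Power at 686: without / with | Power at 720: without / with |
|---|---|---|---|---|
| 30% | 13.0% | 0.46 | 86.0% / 86.0% | 86.6% / 87.0% |
| 50% | 11.7% | 0.44 | 84.8% / 87.2% | 86.7% / 88.8% |
| 70% | 10.4% | 0.39 | 84.2% / 89.9% | 86.7% / 92.0% |
| 90% | 9.1% | 0.29 | 85.1% / 96.7% | 87.2% / 97.4% |

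The Monte Carlo standard error is √(0.85·0.15/4000) ≈ 0.6 points, so the spread in the unadjusted column at 686 is simulation noise around 85%. The gain at 686 runs from 0 to about 12 points, and is about 2 to 6 points for q of 50% to 70%.

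**3. Chance imbalance.** With 343 per arm, the between-arm difference in baseline users has SD √(2·0.06·0.94/343) = 1.8 points, and 1.96 SD is 3.6 points. An imbalance of that size moves the unadjusted risk difference by 0.0355·(q − r): 0.6 points at q = 30% and 2.9 points at q = 90%. The stipulated effect is 7 points. The standard error of the unadjusted difference, √(0.1855/343) = 2.3 points, already contains this variation.

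**4. Hospital.** Section 5.1.5 assigns surgeon codes within a hospital ("each participating surgeon within that hospital must draw one number"), so surgeon is nested in hospital. Assuming 14 hospitals with 3 surgeons each, hospital terms were added to a model that already had a surgeon random effect. Power went from 84.4% to 84.8% (log-odds SDs 0.3 for hospital and 0.2 for surgeon, 500 runs) and from 87.3% to 88.0% (SDs 0.6 and 0.3, 300 runs). Type I error in the first setting was 4.2% v 4.4%. None of these differences is material.

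**The case against.** The strongest reply is that 7.1 is the statistical section and names a single main analysis, while 6.6.3 is general, gives its variables as examples and does not mention the main model. A surgeon random effect also shrinks towards zero when surgeons do not differ, so the two surgeon statements may agree in practice. A statistical analysis plan may settle both matters. This softens the conflict but does not remove it: two of the three baseline variables in 6.6.3 reach the model, the third does not, and one surgeon rule depends on the data while the other does not.

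The reply is also right that the gain may be small. Section 6.6.3 and appendix 17.4 have continued ARM use questioned at follow-up, so high persistence cannot be presumed. At 30% persistence there is no gain.

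A reader might infer more than the protocol supports:

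- **That the trial loses power.** It does not fall below plan. The sample size comes from an unadjusted test, and 720 evaluable patients exceed the 686 required.
- **That the result would be biased.** Under randomization the comparison without baseline ARM remains valid. Chance imbalance affects precision and is already in the standard error.
- **That leaving hospital to a sensitivity analysis forfeits power or balance.** Blocks run within hospitals, the surgeon term absorbs most between-hospital variation, and the simulated difference is under 1 point of power.
- **That the model will be chosen after seeing the data.** The inconsistent wording leaves that possible but does not show it, since 7.1 does name one main analysis.

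**Conclusion.** The point holds as an inconsistency between 6.6.3 and 7.1 and as a missed improvement in the primary model. It should be corrected, but it does not threaten the validity of the trial or its planned 85% power.

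The textual mismatch is certain. The size of the benefit is not: the power gain rests on the assumed persistence of ARM use, a common odds ratio across baseline users and non-users, and the 7.2 rates of 6%, 14% and 7%. The surgeon mismatch is one of wording, and no numerical effect has been shown for it.

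**What to change.** In 7.1, list preoperative ARM use (yes/no) in the main logistic mixed model together with age, smoking and surgeon. In 6.6.3, remove the condition that surgeons are adjusted for only where differences appear, and refer to the model in 7.1 so that both sections state the same one. Keep the present model, without baseline ARM, as a sensitivity analysis. The planned hospital sensitivity analysis can remain unchanged.

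No extra data are needed, because patients with missing baseline data are already excluded. Under section 9 the amendment needs agreement in the steering committee and ethics approval. The one statistical cost is that the conditional odds ratio being estimated changes, for example from about 0.46 to 0.39 at 70% persistence. The report should therefore state which covariates the odds ratio is conditional on.
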